9.6.7. Recording Infusion-Related Reactions

The symptoms of infusion-related reactions may include but are not limited to fever, chills/rigor, nausea, pruritus, angioedema, hypotension, headache, bronchospasm, urticaria, rash, vomiting, myalgia, dizziness, or hypertension. Severe reactions may include acute respiratory distress syndrome, myocardial infarction, ventricular fibrillation, or cardiogenic shock. Individual signs and symptoms of an infusion reaction should be recorded each as a separate AE in the eCRF and identified as an infusion-related reaction. Refer to the eCRF completion guidelines for details.

9.7. Management of Infusion-Related Reactions and Severe Hypersensitivity

As a routine precaution, following completion of study drug(s) administration, patients must be monitored for at least 2 hours after the infusion of study drug in a setting where emergency medical equipment and staff who are trained to respond to medical emergencies are available.

The management for infusion-related reactions, and severe hypersensitivity reactions, according to the NCI-CTCAE criteria are outlined in the following subsections.

9.7.1. Managing Infusion-Related Reactions

The symptoms of infusion-related reactions include but are not limited to fever, chills/rigor, nausea, pruritus, angioedema, hypotension, headache, bronchospasm, urticaria, rash, vomiting, myalgia, dizziness or hypertension. Severe reactions may include acute respiratory distress syndrome, myocardial infarction, ventricular fibrillation, and cardiogenic shock.

Patients should be closely monitored for infusion-related reactions. Immediate access to an ICU or equivalent environment and appropriate medical therapy (including epinephrine, corticosteroids, intravenous antihistamines, bronchodilators, and oxygen) must be available to treat infusion-related reactions.

Treatment modifications for symptoms of infusion-related reactions due to study drug(s) are provided in [Table 3](#).

Table 3: Treatment Modifications for Symptoms of Infusion-Related Reactions Due to Study Drug

NCI-CTCAE grade	Treatment modification for Study Drug
Grade 1 - mild Mild transient reaction; infusion interruption not indicated; intervention not indicated.	Decrease infusion rate by 50%. Any worsening is closely monitored. Medical management as needed.
Grade 2 - moderate Therapy or infusion interruption indicated but responds promptly to symptomatic treatment (eg, antihistamines, nonsteroidal anti-inflammatory drugs, narcotics, intravenous fluids); prophylactic medications indicated for ≤ 24 hours.	Stop infusion. Infusion may be resumed at 50% of previous rate once infusion-related reaction has resolved or decreased to Grade 1 in severity within 2 hours of the infusion interruption. The patient should be discontinued from study drug if the Grade 2 infusion-related reaction has not resolved or decreased over 2 hours of the infusion interruption. Any worsening is closely monitored. Proper medical management should be instituted as described below.
Grade 3 – severe Prolonged (eg, not rapidly responsive to symptomatic medication and/or brief interruption of infusion); recurrence of symptoms following initial improvement; hospitalization indicated for clinical sequelae.	Immediately stop the infusion. Proper medical management should be instituted as described below. The patient should be withdrawn from study drug treatment.
Grade 4 – life-threatening Life-threatening consequences; urgent intervention indicated.	Immediately stop the infusion. Proper medical management should be instituted as described below. The patient should be withdrawn from study drug treatment. Hospitalization is recommended.

Abbreviations: NCI-CTCAE, National Cancer Institute-Common Terminology Criteria for Adverse Events.

NCI-CTCAE Grade 1 or 2 infusion reaction: Proper medical management should be instituted, as indicated per the type of reaction. This includes but is not limited to an antihistamine (eg, diphenhydramine or equivalent), antipyretic (eg, paracetamol or equivalent), and, if considered indicated, oral or intravenous glucocorticoids, epinephrine, bronchodilators, and oxygen.

NCI-CTCAE Grade 3 or 4 infusion reaction: Proper medical management should be instituted immediately, as indicated per type and severity of the reaction. This includes but is not limited to oral or intravenous antihistamines, antipyretics, glucocorticoids, epinephrine, bronchodilators, and oxygen.

9.7.2. Severe Hypersensitivity Reactions

If hypersensitivity reaction occurs, the patient must be treated according to the best available medical practice as described in the complete guideline for emergency treatment of anaphylactic reactions according to the Working Group of the Resuscitation Council (United Kingdom) (Soar et al 2008). Patients should be instructed to report any delayed reactions to the investigator immediately.

In the event of a systemic anaphylactic/anaphylactoid reaction, the infusion must be stopped immediately and the patient discontinued from the study. Systemic anaphylactic/anaphylactoid reactions typically manifest within minutes following administration of the drug/antigen and are characterized by respiratory distress; laryngeal edema; and/or intense bronchospasm; and are often followed by vascular collapse or shock without antecedent respiratory difficulty; cutaneous manifestations such as pruritus and urticaria with/without edema; and gastrointestinal manifestations such as nausea, vomiting, crampy abdominal pain, and diarrhea.

The patient will be administered epinephrine injection and dexamethasone infusion if hypersensitivity reaction is observed. The patient should then be placed on monitor immediately and an ICU should be alerted for possible transfer if needed.

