5.4. Dose Interruption or Modification

There will be no dose reduction of study drug in this study. A dose interruption is an interruption of an infusion.

Each patient will receive a single dose of the study drug via intravenous infusion. The infusion may be temporarily interrupted due to infusion-related reactions or other medical events.

If the AE is resolved or recovered to Grade 1 (whichever is more severe), the infusion should be resumed within 2 hours of the infusion interruption. If the patient is unable to resume the study drug within 2 hours of the infusion interruption, then the patient should be discontinued from the study treatment.

The treatment modification for infusion-related reactions is provided in Section 9.7.1.

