5.5. Blinding

In this study, patients will be randomized to receive BGB-DXP593 or matched placebo in a double-blind fashion. The single dose of study drug will be prepared by an unblinded pharmacist. At the study sites, only the unblinded pharmacist for study drug preparation will know the treatment allocation of patients; other members who are directly involved in the clinical conduct of the study, including the staff for study drug administration, will not know. Both the intravenous infusion of BGB-DXP593 and placebo will be colorless. All the follow-up evaluations will be performed by blinded study site staff. It is imperative to maintain the blind to patient treatment assignment such that neither the investigator, nor the patient, nor medical or ancillary medical staff (except for the unblinded pharmacist who is responsible for the preparation of the study drug and has access to dispensation records), nor the blinded sponsor staff or its designees will know which study drug is being administered. Due to the ongoing need to assess safety, a limited number of sponsor staff will not be blinded to patient treatment assignment (see Section 11.1).

Every effort should be made to avoid unblinding the patient's treatment assignment unless necessary. Unblinding may be indicated and permissible only in specific situations as described below and if necessary, for the patient's welfare. Unblinding would occur through Interactive Response Technology (IRT) as per the instructions in the IRT site user manual. If unblinding has occurred, the sponsor must be notified immediately using the Unblinding Event Form. To ensure the continued blinding of study personnel, this form will not include the treatment assignment. Patients will remain on study for study follow-up.

The study will be unblinded after primary analysis database lock.

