7.5. Discontinuation From Study Treatment or From the Study

7.5.1. Patient Discontinuation From Study Treatment

Eligible patients will receive a complete dose of study drug. Patients have the right to discontinue study treatment infusion for any reason. In addition, the investigator has the right to discontinue a patient from study treatment. Patients who discontinue study treatment will remain on the study and continue to be followed for protocol-specified follow-up procedures ([Appendix 1](#)), if possible; this will include, but is not limited to, the safety assessments.

The primary reason for discontinuation from study treatment should be documented on the appropriate eCRF. Patients may discontinue study treatment for reasons including but not limited to the following:

- The investigator or sponsor determines it is in the best interest of the patient
- Significant or persistent adverse event(s)

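### Section 9.7.2 takes a patient with systemic anaphylaxis off the study, not just off study treatment, so planned swabs and later AE recording are lost for no stated reason

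*Protocol*

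**What the plan says.** Protocol Section 9.7.2 deals with severe hypersensitivity. For a systemic anaphylactic or anaphylactoid reaction it states that "the infusion must be stopped immediately and the patient discontinued from the study". The same section adds: "Patients should be instructed to report any delayed reactions to the investigator immediately".

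The other provisions on stopping the drug end treatment only:

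- Section 5.4, when an interrupted infusion cannot be restarted within two hours: "then the patient should be discontinued from the study treatment".
- Section 9.7.1, Table 3, Grade 3 infusion-related reaction: "The patient should be withdrawn from study drug treatment".
- Section 9.7.1, Table 3, Grade 4 (life-threatening) reaction: "The patient should be withdrawn from study drug treatment. Hospitalization is recommended".
- Section 7.5.1, the general rule: "Patients who discontinue study treatment will remain on the study and continue to be followed for protocol-specified follow-up procedures". This is qualified by *if possible*.

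Section 5.5 follows the same principle for a patient whose assignment has been unblinded: "Patients will remain on study for study follow-up".

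Section 7.5.2 lists reasons for leaving the study. The list is expressly open and names neither an adverse event nor anaphylaxis.

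**The concern.** The protocol separates stopping the drug from leaving the study and, with one exception, keeps the patient on study when the drug is stopped for a reaction. The exception is a severe reaction to the drug. With a single infusion there is no further dose to withhold, so leaving the study protects the patient from nothing that stopping the infusion has not already dealt with.

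Two things are at stake. The first is missing data created by the protocol itself. The patient was randomized and stays in the ITT set, but gives no post-baseline swab, and the cause is a reaction to treatment. The second is thinner observation after a severe hypersensitivity reaction. There are fewer scheduled AE visits, a shorter period in which all AEs are recorded, and no ADA sample at or after Day 15.

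**Working it through.** The point rests on comparing texts; the plan gives no figure for it. The arithmetic only sizes the consequence.

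**Step 1. The provisions side by side.**

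| Situation | Section | Drug | Study participation |
|---|---|---|---|
| Infusion cannot be resumed within 2 hours | 5.4 | stopped | continues under 7.5.1, if possible |
| Grade 3 or 4 infusion-related reaction | Table 3 | stopped | continues under 7.5.1, if possible |
| Unblinded patient | 5.5 | not addressed | continues |
| Systemic anaphylaxis | 9.7.2 | stopped | ends |

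**Step 2. What one patient loses after a Day 1 reaction.** Leaving the study triggers an End-of-Study Visit within 7 days (Section 7.4.1), so by about Day 1 + 7 = Day 8, and a Day 31 visit (Section 7.4.2). No sentence says that the other visits lapse. That is inferred from leaving the study together with Appendix 1, whose layout is partly broken in the text available.

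- *Nasopharyngeal swabs.* The row is marked at Day 1 predose and Days 3, 8 and 15, with no mark at the End-of-Study or Day 31 visit. Post-baseline swabs go from 3 to 0.
- *Scheduled AE assessments.* After Day 1 the row is marked at Days 3, 8, 15, 29, 85 and 113, which is 6 visits. They are replaced by 2: End-of-Study by about Day 8, and Day 31.
- *Recording of all AEs.* Section 9.6.1 runs it to the later of 30 days after treatment and the End-of-Study Visit. On study, that is about Day 113. Off study, the End-of-Study Visit comes by about Day 8, so the 30-day limit applies, which is Day 31. The difference is about 113 − 31 = 82 days, during which only SAEs considered drug-related are reported.
- *ADA* (Appendix 2; only at sites able to sample). Post-dose samples are due on Days 15, 29 and 113, which is up to 3. One sample is taken at the early End-of-Study Visit, so 3 becomes 1, and that one precedes the first scheduled post-dose sample.

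**Step 3. How many patients.** The documents give no anaphylaxis rate. I assume 0.1% to 1% of patients on active drug. Active patients: 3 × 43 = 129.

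- Expected cases: 129 × 0.001 = 0.13; 129 × 0.01 = 1.29.
- Chance of no case: 0.999^129 = 0.879; 0.99^129 = 0.273.
- Chance of exactly one: 129 × 0.001 × 0.999^128 = 0.113; 129 × 0.01 × 0.99^128 = 0.356.
- Chance of at most one: 0.992; 0.630 (summed before rounding).

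**Step 4. Effect on the primary analysis.** The plan needs 41 evaluable patients per arm and randomizes 43, so each arm can lose 43 − 41 = 2. As a stress test beyond that allowance, I simulated the maximum-contrast test with doses 0, 5, 15 and 30, the five listed shapes, a maximum effect of 1.5, an SD of 3.2 and one-sided 5%. I then removed one further patient from every active arm (41/40/40/40 against 41 per arm). Power fell by 0.2 to 0.7 points depending on shape; for the sigmoid Emax shape it went from 82.4% to 81.8%. Removing three per active arm (41/38/38/38) took that shape to 80.3%. Only these differences are used here. Under the other four shapes the simulated starting power at 41 per arm was about 70% to 72%, below the stated 82%, but that is a separate matter.

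**The case against.** The strongest reply is that Section 9.7.2 is a specific medical rule, not a slip. Section 9.7 announces two categories ("The management for infusion-related reactions, and severe hypersensitivity reactions, according to the NCI-CTCAE criteria are outlined in the following subsections"), a specific rule can override a general one, Section 7.5.1 is itself qualified, and the open list in Section 7.5.2 does not bar removal for anaphylaxis. This stands in part. A reader might infer that the protocol contradicts itself or that Section 7.5.2 forbids the rule, and the documents do not support either. What remains is an exception without a reason.

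A possible reason is that Section 9.7.2 calls for dexamethasone while Section 6.2 lists corticosteroids among prohibited drugs. This does not explain the rule, because Section 9.7.1 also provides glucocorticoids for Grade 3 and 4 infusion reactions and those patients stay on study.

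A reader might also infer that safety follow-up is abandoned. It is not. Section 9.3.4 requires active follow-up of every AE until it resolves or stabilizes, all AEs are recorded for at least 30 days, and drug-related SAEs are reported after that. This also covers delayed reactions reported by the patient. TEAEs are counted only to 30 days after dosing, and of the four scheduled AE visits in that window (Days 3, 8, 15 and 29), Days 8 and 29 have near equivalents in the early End-of-Study and Day 31 visits. Counting all nine later contacts in Appendix 1 as lost safety visits would overstate the loss: Days 5, 22 and 57 are by phone or video and carry no AE mark.

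Nor can anaphylaxis be called the most serious reaction foreseen, since Section 9.7.1 names myocardial infarction, ventricular fibrillation and cardiogenic shock among severe infusion reactions.

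**Conclusion.** The point holds as a cheap improvement. Section 9.7.2 ends study participation where the comparable provisions end only treatment; it gives no reason, and with a single dose it adds no protection. The cost per affected patient is all three post-baseline nasopharyngeal swabs, scheduled AE visits at Days 3 and 15 and after Day 31, about 82 days of all-AE recording, and up to two ADA samples net, including any at or after Day 15.

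It does not threaten the trial's conclusions, and a reader should not infer that it does. At the assumed rates, zero or one case is the likeliest outcome, eligibility already excludes known component allergy and severe allergic reactions with a reasonable risk of recurring, and losing one more patient in every active arm moves simulated power by less than 1 point. With a baseline sample, the early ADA sample keeps the patient in the ADA Analysis Set, so only later detection is lost.

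This rests on three assumptions: the reaction occurs on Day 1, the site follows Section 9.7.2 literally, and Appendix 1 has been read correctly from the extracted table. The event rate is assumed, not documented.

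**What to change.** In Protocol Section 9.7.2, change the closing instruction of the sentence quoted above so that it reads: *the patient discontinued from study treatment; the patient remains on study and continues scheduled follow-up per Section 7.5.1, if possible*.

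This is one phrase. Emergency management is unchanged and the SAP needs no edit. The only downside is continued visits for the few patients affected, who may still withdraw consent under Section 7.5.2. If removal from the study was intended, a sentence giving the reason would settle the inconsistency, though it would not recover the data.

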10. STATISTICAL METHODS AND SAMPLE SIZE DETERMINATION

A statistical analysis plan (SAP) will be prepared and finalized prior to database lock. This document will provide further details regarding the definition of analysis variables and analysis methodology to address all study objectives. Any deviations in the planned analysis as stated in the protocol will be delineated in the SAP. Any deviations from the SAP will be reported in the clinical study report. A data review will be conducted prior to database lock.

10.1. Statistical Analysis

10.1.1. Analysis Sets

The Intent-to-Treat (ITT) Analysis Set includes all randomized patients. Patients will be analyzed according to the treatment assigned at randomization. This will be the primary analysis set for efficacy analyses.

The Safety Analysis Set includes all patients who have received the study drug (BGB-DXP593 or placebo). Patients will be analyzed according to their actual treatment received. The Safety Analysis Set will be used for all safety analyses.

The PK Analysis Set includes all patients who have received the study drug (BGB-DXP593) per the protocol and for whom any postdose PK data are available.

The ADA Analysis Set includes all the patients who have received the study drug and in whom both baseline ADA and at least 1 postbaseline ADA results are available.

10.1.2. Randomization Methods

Patients will be randomized using the IRT system with allocation ratio of 1:1:1:1 to placebo, BGB-DXP593 at 5 mg/kg, BGB-DXP593 at 15 mg/kg, and BGB-DXP593 at 30 mg/kg. Patient randomization will be stratified by country and disease severity (mild versus moderate COVID-19).

10.1.3. Patient Disposition

The number of patients randomized, treated, discontinued from study drug and/or the study will be counted. The primary reason for study drug and/or study discontinuation will be summarized according to the categories in the eCRF.

Important protocol deviations will be summarized and listed by category.

10.1.4. Demographic and Other Baseline Characteristics

Demographic and other baseline characteristics will be summarized using the ITT Analysis Set and descriptive statistics. Continuous variables include but are not limited to age, weight, and height. Categorical variables include but are not limited to gender, geographical region, and race.

10.1.5. Prior and Concomitant Medications

Prior medications will be defined as medications that stopped before the administration of study drug. Concomitant medications will be defined as medications that 1) started before the administration of study drug and were continuing at the time of the administration of study drug, or 2) started on or after the date of the administration of study drug up to 30 days after dosing.

Concomitant medications will be coded using the World Health Organization Drug Dictionary drug codes and will be further coded to the appropriate Anatomical Therapeutic Chemical code indicating therapeutic classification. Prior and concomitant medications will be summarized and listed by drug and drug class. A listing of prior and concomitant medications will be provided.

10.2. Efficacy Analyses

10.2.1. Primary Endpoint Analyses

The statistical hypotheses to be tested for the primary endpoint are as follows:

H₀: there is a flat dose response curve comparing change from baseline to Day 8 in SARS-CoV-2 viral shedding in the placebo and the BGB-DXP593 dose groups

H₁: there is a non-flat dose response curve indicating a benefit of BGB-DXP593 over placebo

A Mixed Model Repeated Measures (MMRM) analysis will be used to analyze the primary endpoint of change from baseline to Day 8 in SARS-CoV-2 viral shedding. This model will include treatment, visit, and disease severity as discrete fixed effects; baseline viral shedding as a continuous fixed effect; and interaction between visit and treatment, interaction between visit and baseline, interaction between visit and disease severity, and patient as a random effect. The primary treatment comparisons will be the contrast between treatments at Day 8.

[figure not shown]
The analysis will be carried out and covariate-adjusted fixed effect estimates of average response for each treatment and the covariance matrix will be extracted from the fit and used for multiple comparison procedures and modelling approaches (MCPMod) analysis.

The primary analysis uses methodology for dose finding employing both multiple comparison procedures and modelling techniques. The MCPMod procedure allows for simultaneous evaluation of different potential dose response patterns, whilst protecting the overall probability of Type I error (one-sided α of 5%).

For the hypothesis testing and for the sample size calculation, the basic shape of each of the models to be tested must be predefined. The following models will be considered for this analysis: linear, Emax, SigEmax and quadratic.

The model assumptions and resulting graphs were selected to cover both plausible and a diverse range of dose response patterns. These are shown in [Figure 3](#). The parameters for each model shape are listed in [Table 4](#).

Figure 3: Shape of the Considered Dose Response Patterns for the MCPMod Analysis

Abbreviation: MCPMod, multiple comparison procedures and modelling approaches

Table 4: Parameter(s) in Each Model

Model	Prespecified parameters
Emax1	$ED_{50} = 2.6$
Emax2	$ED_{50} = 12.5$
sigEmax	$ED_{50} = 10, h = 4$
Quadratic	$\delta = -0.022$
Linear	No assumption needed

If at least one model is statistically significant, then we will reject the null hypothesis of a flat dose response relationship over viral shedding change at Day 8, with a multiple contrast test controlled for the family-wise type I error rate at one-sided $\alpha = 5\%$.

After rejecting the null hypothesis, the statistically significant model(s) from the above candidate set are selected as reference models. The dose-response relationship is estimated using model average technique to generate the new estimates.

The target dose(s) can be estimated from the average model by incorporating information on the minimum clinically relevant effect and by accounting for safety.

Comparisons of active doses to placebo (90% confidence intervals [CIs] and p-values) based on the mixed effects model will be reported. These are supportive analyses of the primary endpoint to supplement the MCPMod analysis, which is the primary analysis.

